#### Abdominal Pain

The abdominal pain score is captured from diary entries of subjects recording the level of worst abdominal pain experienced over 24 hours using a numeric rating scale (range 0 to 10; 0 = No pain and 10 = worst possible abdominal pain). A higher score indicates a higher level of abdominal pain.

#### Bowel Urgency

Bowel urgency is captured from diary entries of subjects recording the presence (yes/no) of bowel urgency over 24 hours.

### Tablet Based

The IBDQ will be collected electronically via a Tablet device into which the subject will directly enter the required pieces of information while at the site. The electronic device will be programmed to allow data entry for only the visits specified in the protocol and will not allow for subjects to complete more than one of the same assessment at any one visit. All data entered on the device will be immediately stored to the device itself and (manually/automatically) uploaded to a central server administrated by CRF

Health. The investigational site staff will be able to access all uploaded subject entered data via a password protected website, up until the generation, receipt and confirmation of the study archive.

#### IBDQ

The IBDQ is a widely used questionnaire for health-related quality of life (QoL) assessment in patients with inflammatory bowel diseases (IBD). It consists of 32 items categories into 4 dimensions: "bowel symptoms," "systemic symptoms," "social function," and "emotional function." Item responses are graded on a 7-point Likert scale, with 1 being most severe and 7 being no problem at all. A higher score indicates a better health status.

### 3.5 Pharmacokinetic Sampling

---

On the day of the study visit, subjects will be administered the ravagalimab intravenous (IV) or subcutaneous (SC) dose and blood samples for pharmacokinetic (PK) and ADA assessments should be collected at the specified time points at each visit as follows:

For PK samples:

- At Baseline (Week 0) at the end of the ravagalimab IV infusion
- At Weeks 2, 4, 8, 12, and 52 prior to administration of ravagalimab SC dose
- At Week 104 or in the event of PD at any time during the visit.

For ADA and nAb samples:

- At Baseline (Week 0) at any time during the visit
- At Weeks 4, 12, and 52 prior to administration of ravagalimab SC dose
- At Week 104 or in the event of PD at any time during the visit.

The date and time of sample collection will be captured on the electronic case report form (eCRF).

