Investigational Plan:	
Study M15-722 is a Phase 2a, multicenter, single arm, open-label study to investigate the efficacy and safety of ravagalimab in subjects with moderate to severe UC who failed prior therapy. The study contains a 35-day screening period, 2 treatment periods, and an 84-day follow up period from the last dose of study drug. The induction period is an open-label (OL) 12-week treatment period to evaluate the efficacy, safety, tolerability, pharmacokinetics (PK) and receptor occupancy (RO) of ravagalimab for inducing endoscopic improvement at Week 8. Subjects who achieve clinical response per Partial Adapted Mayo score at Week 12 may continue into the maintenance period. The maintenance period is an OL 92-week treatment period to assess efficacy and safety for maintenance of response with ravagalimab. An internal data monitoring committee (DMC) will review safety at regular intervals.

Key Eligibility Criteria:	
 
Subjects must understand and personally voluntarily sign and date an informed consent, approved by an independent ethics committee (IEC)/institutional review board (IRB), prior to the initiation of any screening or study-specific procedures.
 
Adult male or female, between 18 and 75 years of age, inclusive, at time of the Baseline visit.
 
Diagnosis of UC for at least 3 months prior to Baseline. Appropriate documentation of biopsy results consistent with the diagnosis of UC in the assessment of the Investigator, must be available.
 
Subject meets the following disease activity criteria: Active UC with an Adapted Mayo score of 5 to 9 points and endoscopic subscore of 2 to 3 (confirmed by central review).
 
History of inadequate response, loss of response, or intolerance to one or more of the approved therapies: infliximab, adalimumab, golimumab, vedolizumab, ustekinumab and/or tofacitinib. Dose and duration requirements are specified in Section 5.1.
 

Study Drug and Duration of Treatment:	Ravagalimab (100 mg/mL) Induction Period: 
 
OL ravagalimab 600 mg intravenous (IV) Week 0; ravagalimab 300 mg subcutaneous (SC) Weeks 2, 4, 6, 8, and 10
 
 Maintenance Period: 
 
Open-label ravagalimab 300 mg SC every other week (eow) from Week 12 to Week 102
 

Date of Protocol Synopsis:	04 December 2020

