- p. For the visit when endoscopy will be conducted, stool sample should be collected prior to bowel prep and should be returned to the site within 3 days of collection. If a sample cannot be obtained during the site visit, the site will give instructions and a stool sample supply kit.
- q. Day 1 serum ravagalimab concentrations will be collected at the end of the ravagalimab IV infusion and Day 1 ADA/nAb will be determined from samples collected at any time during the visit. All subsequent samples will be collected just prior to dosing on the study visit. At Week 104 or if a patient prematurely discontinues, serum ravagalimab and/or ADA/nAb will be collected at any time during the visit. The date and time of sample collection will be captured on the electronic case report form (eCRF).
- r. Administration of drug will be performed after all assessments and examinations scheduled for that day have been completed.
- s. CD40 receptor occupancy (RO) and T cells, NK cells and B cell subsets (including plasmablasts) should be collected prior to dose at each visit when applicable.
- t. Only to be collected at PD visit if subject discontinues prior to Week 52.
- u. Where mandated by local requirements; subjects with HBs Ab+ and/or HBc Ab+ and negative HBV DNA at Screening should have HBV DNA PCR testing performed approximately every 12 weeks. HBV DNA PCR testing every 12 weeks is not necessary when the subject has a history of HBV vaccination and is HBs Ab+ and HBc Ab-. If necessary, HBV DNA PCR may be tested at unscheduled visits.

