## 3.11 Administer Study Drug

---

Intravenous study drug will be administered to all subjects on-site. For female subjects of childbearing potential, the urine pregnancy test needs to be negative prior to receiving study drug. The site will be provided administration instructions. Study drug will be administered to subjects beginning at baseline (Day 1) and as specified in Section 2.1. Administration of drug will be performed after all assessments and examinations scheduled for that day have been completed. At the visits specified in Section 2.1, the site personnel will review and retain a copy of the subject diary, review returned study drug kits, and empty study drug packaging to verify compliance. A separate study drug administration guideline will be provided as well.

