## 3.12 Clinical Laboratory Tests

---

The baseline laboratory test results for clinical assessment for a particular test will be defined as the last measurement prior to the initial dose of study drug.

A certified laboratory will be utilized to process and provide results for the clinical laboratory tests. Laboratory reference ranges will be obtained prior to the initiation of the study.

Instructions regarding the collection, processing, and shipping of these samples will be provided by the central laboratory and sent to the following certified laboratory addresses:

For sites in North America:

Covance  
[name] USA

For sites in Europe:

Covance  
[name] Switzerland

Blood samples will be obtained for the laboratory tests listed in the Clinical Laboratory Tests table below. Blood draws should be performed, as much as possible, after efficacy assessments and questionnaires (IBDQ, etc.) and vital sign determinations are obtained during a visit. Blood draws should be performed before study drug administration.

All abnormal laboratory tests that are considered clinically significant by the Investigator will: 1) be followed to a satisfactory resolution, 2) follow the toxicity management instructions for Select Laboratory Abnormalities as applicable (see Section 6.2 of the protocol).

Clinical Laboratory Tests		
Hematology	Clinical Chemistry	Urinalysis

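### The Day 1 ADA/nAb sample may be drawn at any time in the visit, so the immunogenicity baseline can be taken with drug circulating; the general pre-dose texts conflict with this

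*Protocol*

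**What the plan says.** Two provisions in the Operations Manual (Protocol Appendix F) govern when ADA and nAb are sampled.

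- Section 3.5 sets the first sample "At Baseline (Week 0) at any time during the visit" and the on-treatment samples "At Weeks 4, 12, and 52 prior to administration of ravagalimab SC dose".
- Footnote q in Section 2.1 agrees: "Day 1 ADA/nAb will be determined from samples collected at any time during the visit". It continues: "All subsequent samples will be collected just prior to dosing on the study visit". Both places also allow any time at Week 104 or premature discontinuation.

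Day 1 carries the only IV dose (Protocol synopsis: "OL ravagalimab 600 mg intravenous (IV) Week 0"). Its PK sample is fixed "At Baseline (Week 0) at the end of the ravagalimab IV infusion".

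Two general texts point the other way.

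- Section 3.12, whose test table lists serum ADA and nAb, says: "Blood draws should be performed before study drug administration".
- Section 3.11, and footnote r in the same terms, says: "Administration of drug will be performed after all assessments and examinations scheduled for that day have been completed".

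Protocol Section 3.6 plans a descriptive summary of ADA development. SAP Section 1.0 leaves pharmacokinetic and biomarker analyses out of its scope, and the SAP has no rule for a baseline ADA sample taken after dosing.

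**The concern.** ADA development can only be judged against a reference sample. Screening includes no ADA draw, so Day 1 is the only point in the treatment schedule where a drug-free sample can be had, and only if it is drawn before the infusion. Under the specific text, a site can fill the ADA tube at the end-of-infusion PK draw and be fully compliant.

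If circulating drug interferes with the assay, pre-existing antibody could be missed in such a sample and a later positive counted as new. Baselines would also not be comparable across subjects, because some would be drug-free and others drawn just after 600 mg IV. The output at stake is the ADA summary and anything that uses ADA status, including the reading of suspected anaphylaxis, where Section 3.12 of the Operations Manual asks for PK, ADA and nAb samples.

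**Working it through.** The plan states no figure to reproduce. The check sets the texts side by side and then sizes the drug load.

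**1. Which samples are tied to the dose (Operations Manual)**

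| Sample | Stated time | Dose at that visit? |
|---|---|---|
| Day 1 ADA/nAb (3.5, footnote q) | any time | yes, 600 mg IV |
| Weeks 4, 12, 52 ADA/nAb (3.5) | before dosing | yes, SC |
| Week 104 or premature discontinuation ADA/nAb (3.5) | any time | none in the Section 2.1 visit lists |
| Day 1 PK (3.5) | end of infusion | yes |
| Day 1 CD40 receptor occupancy (3.6, footnote s) | before dosing | yes |

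Among scheduled samples, Day 1 is the only dosing visit at which ADA is not tied to the dose. Section 3.6 shows that the authors wrote a pre-dose condition for Day 1 when they wanted one. Samples for suspected anaphylaxis, due within 24 hours of the reaction, also have no pre-dose condition, but they are not scheduled.

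**2. Do the general texts settle it?** Not clearly. The table governed by Section 3.12 also lists the PK sample, which on Day 1 must follow the infusion, so the general rule has at least one exception that day. The ADA wording makes no reference to the general rule. Someone looking up ADA timing in 3.5 or footnote q would find no pre-dose condition.

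**3. Drug present at each ADA time (illustration under assumptions)**

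Concentration at end of infusion = dose / initial volume of distribution. The volume is not in the documents; 2.5 to 5 L is assumed.

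- 600 mg / 2.5 L = 240 µg/mL; 600 / 3 = 200; 600 / 5 = 120.
- Before the infusion: zero. Protocol Section 5.1, criterion 29, bars any earlier ravagalimab treatment.

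Drug in the body before a later dose: A(t) = 600 × 2^(−t/h) + Σ 300 × F × 2^(−(t−tᵢ)/h), where tᵢ are the days of the earlier SC doses. The half-life follows from Operations Manual Section 4.1, which equates 84 days with 5 half-lives: h = 84/5 = 16.8 days. SC bioavailability F is assumed to be 0.5 to 1.0, with each SC dose entering at once.

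| Time | F = 0.5 | F = 0.75 | F = 1.0 | 600 mg ÷ amount |
|---|---|---|---|---|
| Week 4 pre-dose | 273 mg | 315 mg | 357 mg | 2.2 to 1.7 |
| Week 12 pre-dose | 200 mg | 291 mg | 381 mg | 3.0 to 1.6 |

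These are amounts in the body, not serum concentrations. The end-of-infusion load is higher than at later ADA visits, but only by a factor of about 1.6 to 3.0. The contrast that matters is between zero drug and any drug on Day 1, and that does not depend on the assumed volume.

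**4. Effect on the summary.** With 40 evaluable subjects, one misclassified subject moves a treatment-emergent rate by 1/40 = 2.5 percentage points, and k subjects by 2.5 × k. The documents give no basis for k.

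**The case against.** The strongest reply is that the ADA wording can be read together with Sections 3.11 and 3.12, so that any time in the visit means any time before dosing. One explicit PK exception does not cancel the general rule for other Day 1 samples, and receptor occupancy is kept pre-dose that same day. This stands in part. A reader might infer that the general rules cannot apply on Day 1 at all; the documents do not support that. They show a conflict that the text does not resolve.

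Second, the harm needs four things together: pre-existing antibody, a post-infusion draw, an assay masked at that drug level, and a later positive. Neither drug tolerance nor the prevalence of pre-existing antibody is given, and no subject has had ravagalimab before. The last two conditions also pull against each other: Week 4 and Week 12 samples contain substantial drug, so an assay masked on Day 1 may be impaired then too, and one that works then may tolerate Day 1. This stands in full and makes misclassification a risk, not a shown result.

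Third, sample date and time are captured on the eCRF, and ADA handling may be set in laboratory or analysis documents not available here. The time stamp does identify late samples, but it cannot recover a pre-dose result.

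Fourth, it may seem natural to discard every Day 1 sample drawn after the infusion began. That would be wrong: a first exposure does not induce antibody within hours, so a positive still shows pre-existing antibody. Only negatives are uncertain.

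**Conclusion.** The point holds as a conflict in the text with a conditional consequence. The specific ADA wording, stated twice, permits a baseline drawn after 600 mg IV; the general wording asks for blood before dosing; and nothing says which prevails. If the assay is drug-sensitive, a post-infusion baseline could be falsely negative and a later positive could be labelled treatment-emergent. The size is 2.5 percentage points per affected subject at 40 evaluable subjects, with the number affected unknown. The concentration and drug-load figures rest on the assumed volume and bioavailability and serve only as illustration.

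A reader might go further and infer that baselines will be masked, or that the ADA results will be unusable. The documents do not support either: they give no assay tolerance, no prevalence of pre-existing antibody and no record of when sites draw the sample. The primary endpoint does not use ADA status and is unaffected. The change is still worth making, because it secures the only possible drug-free ADA reference in the schedule at almost no cost.

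**What to change.** In Operations Manual Section 3.5 and footnote q, state that the Day 1 ADA/nAb sample is collected before the start of the ravagalimab infusion, and keep the end-of-infusion time for the PK sample only. In Section 3.12, name the Day 1 PK sample as the exception to the pre-dose rule so that the texts agree.

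For subjects already enrolled:

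- Use the eCRF sample time to flag any Day 1 ADA/nAb sample taken after the infusion started.
- Keep a flagged positive as baseline positive.
- Treat a flagged negative as baseline status unknown.
- Report the treatment-emergent ADA summary with and without the subjects of unknown baseline status.

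Put these rules in whichever document governs the ADA analysis, since the SAP does not cover it.

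The cost is a wording change in a few places, a matching laboratory-manual note if needed, and one extra presentation of a descriptive table. No extra venipuncture is needed, because the Day 1 receptor-occupancy sample must already be drawn before dosing. Day 1 chemistry and hematology should not be relied on for this: footnote o requires them only if more than 14 days have passed since Screening or health status has changed.

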### 3.6 Biomarker Sampling

---

Blood samples will be collected for biomarker research at the designated study visits as specified in Section 2.1. Biopsies for biomarker analysis will be done when performing endoscopies. Up to 4 biopsies will be taken at each visit with endoscopy for biomarker research; 1 biopsy for histologic assessment by central review, 1 biopsy for gene expression analysis (including CD40 signature), 2 biopsies for tissue RO (where applicable). Collection of biomarker samples should occur prior to administration of drug on treatment days when applicable. Whole blood for CD40 RO and/or analysis of T cells, NK cells and B cell subsets (including plasmablasts) will be collected prior to drug administration at Baseline, Week 4, Week 8, and Week 12; and at any time during the visit at Week 52 or in the event of PD prior to Week 52. All biomarker samples should be collected, labeled, and shipped as outlined in the study-specific laboratory manual. AbbVie (or people or companies working with AbbVie) will store

the samples and data in a secure storage space with adequate measures to protect confidentiality. The samples may be retained while research on ravagalimab (or drugs of this class) or UC and related conditions continues, but for no longer than 20 years after study completion, or per local requirement.

### 3.7 12-Lead Electrocardiogram

---

A 12-lead ECG will be performed at the designated study visits as specified in Section 2.1. For subjects with a normal ECG taken within 90 days of Screening, a repeat ECG at Screening will not be required, provided source documentation is available. Subjects can have a repeat ECG at any time during the study as warranted based on the opinion of the Investigator. The ECG should be performed prior to blood collection.

The ECGs will be evaluated by an appropriately trained physician at the site ("local reader"). The local reader from the site will sign and date all ECG tracings and will provide his/her global interpretation as a written comment on the tracing using the following categories:

- Normal ECG
- Abnormal ECG – not clinically significant
- Abnormal ECG – clinically significant

Only the local reader's evaluation of the ECG will be collected and documented in the subject's source folder. The automatic machine reading (i.e., machine-generated measurements and interpretation that are automatically printed on the ECG tracing) will not be collected.

ECGs with QT interval corrected for heart rate using Fridericia's correction formula (QTcF) should be reported (or calculated) and documented in the source documents and later transcribed on to the appropriate eCRF if QTcF prolongation is observed.

A valid QTcF cannot be calculated in subjects who have a pacemaker or supraventricular or ventricular conduction abnormalities. In cases of QTcF prolongation, the baseline QTcF will need to be entered into the appropriate eCRF for comparison as well. In addition, any clinically significant findings will be documented in the source documents and later transcribed on to the appropriate eCRF. Each signed original ECG will be monitored by the responsible site monitor and kept with subject's source documents onsite.

### 3.8 Height and Weight

---

Height will be measured at screening only. Body weight will be measured at scheduled visits as specified in Section 2.1 and before blood draws are performed. The subject will wear lightweight clothing and no shoes during weighing.

## 3.9 Vital Signs

---

Vital sign determinations of systolic and diastolic blood pressure, pulse rate, and body temperature will be obtained at visits as specified in Section 2.1. Blood pressure and pulse rate should be measured after the subject has been sitting for at least 3 minutes. Blood pressure, pulse rate, temperature, and respiratory rate should be performed before blood draws are performed.

## 3.10 Physical Examination

---

A complete physical examination, including an assessment of EIMs, will be performed at the designated study visits as specified in Section 2.1. The physical examination performed on Study Day 1 will serve as the baseline physical examination for the entire study. Any significant physical examination findings after the first dose will be recorded as adverse events. All findings, whether related to an AE or part of each subject's medical history, will be captured on the appropriate eCRF page.

At any time, a symptom-directed physical examination can be performed as deemed necessary by the investigator.

## 3.11 Administer Study Drug

---

Intravenous study drug will be administered to all subjects on-site. For female subjects of childbearing potential, the urine pregnancy test needs to be negative prior to receiving study drug. The site will be provided administration instructions. Study drug will be administered to subjects beginning at baseline (Day 1) and as specified in Section 2.1. Administration of drug will be performed after all assessments and examinations scheduled for that day have been completed. At the visits specified in Section 2.1, the site personnel will review and retain a copy of the subject diary, review returned study drug kits, and empty study drug packaging to verify compliance. A separate study drug administration guideline will be provided as well.

## 3.12 Clinical Laboratory Tests

---

The baseline laboratory test results for clinical assessment for a particular test will be defined as the last measurement prior to the initial dose of study drug.

A certified laboratory will be utilized to process and provide results for the clinical laboratory tests. Laboratory reference ranges will be obtained prior to the initiation of the study.

Instructions regarding the collection, processing, and shipping of these samples will be provided by the central laboratory and sent to the following certified laboratory addresses:

For sites in North America:

Covance  
[name] USA

For sites in Europe:

Covance  
[name] Switzerland

Blood samples will be obtained for the laboratory tests listed in the Clinical Laboratory Tests table below. Blood draws should be performed, as much as possible, after efficacy assessments and questionnaires (IBDQ, etc.) and vital sign determinations are obtained during a visit. Blood draws should be performed before study drug administration.

All abnormal laboratory tests that are considered clinically significant by the Investigator will: 1) be followed to a satisfactory resolution, 2) follow the toxicity management instructions for Select Laboratory Abnormalities as applicable (see Section 6.2 of the protocol).

Clinical Laboratory Tests		
Hematology	Clinical Chemistry	Urinalysis
Hematocrit Hemoglobin Red Blood Cell (RBC) count White Blood Cell (WBC) count Platelet count Diff. Automatic (absolute count): Neutrophils Eosinophils Basophils Monocytes Lymphocytes Manual Differential (ONLY IF Automated Differential is abnormal): Neutrophils, bands (Stabs) Neutrophils, polymorphonuclear Eosinophils Basophils Monocytes Lymphocytes	Enzymes Aspartate transaminase (AST, GOT) Alanine transaminase (ALT, GPT) Alkaline Phosphatase Creatine Kinase Electrolytes Calcium Sodium Potassium Chloride Bicarbonate Substrates Blood urea nitrogen Creatinine Bilirubin Total Bilirubin Direct (if total is elevated) Bilirubin Indirect (if total is elevated) Albumin Cholesterol, total Low-density lipoprotein (LDL)-Cholesterol High-density lipoprotein (HDL)-Cholesterol Triglycerides Glucose	Dipstick Urinalysis (local) Urine Nitrite Urine Protein Urine Glucose Urine Ketone Urobilinogen Urine Bilirubin Urine RBC/Erythrocytes Urine WBC/Leukocytes Urine pH Urine creatinine Urine-Sediment (microscopic examination, only if urine analysis abnormal) Urine Sediment Bacteria Urine Cast in Sediment Urine Squamous Epithelial Cells Urine Sediment Crystals, Unspecified Urine Sediment RBC/Erythrocytes Urine Sediment WBC/Leucocytes Urine Urine Albumin-to-Creatinine Ratio
Stool Samples	Coagulation	Other Tests
C. difficile toxin Fecal calprotectin (FCP)	INR a	Urine Pregnancy test b (local) Serum Pregnancy test b Tryptase c Histamine c Hepatitis B screening Hepatitis C screening HIV test SARS-CoV-2 molecular test, if applicable
PK/Immunogenicity	Biomarkers	Biopsy
Serum ravagliimab concentration c Serum ADA c and nAb c	high-sensitivity C-reactive protein (hs-CRP) CD40 receptor occupancy (RO) Plasmablast frequency Exploratory biomarker research	Histopathology scoring Tissue RO (if applicable) Gene expression

a. INR test only drawn if ALT or AST > 3 × ULN (upper limit of normal) and Total Bilirubin < 2 × ULN. Refer to Section 6.2 in the protocol for more information.

b. Pregnancy testing is not required for women of nonchildbearing potential.

c. To be done with the occurrence of a suspected anaphylaxis.

